12.14 Appendix 14: Risk assessment (version 1: 20/12/2021)

Edinburgh Napier University RISK ASSESSMENT FORM

SCHOOL/SERVICE: School of Health and Social Care LOCATION: Sighthill DATE: 21/12/2021

Description of event/activity: Cross-sectional and qualitative study.

No.	Hazards identified	People at risk from	Existing control		Risk	_	Further action / recommendations	Action	Action	Completed
1	Risk Physical threat or abuse	hazards Researcher	Patient research will take place in hospital environment so existing hospital operating procedures will be adhered to. Healthcare professional research is by telephone.	Н	М	X	Planning research to minimise risks Effective means of communication If deemed high risk researcher must not work alone Dress appropriately Emergency plan in place Staff training in confrontation etc.	by whom N/A	by when	
2	Risk of physiological trauma	Researcher	Patient research will take place in hospital environment so existing hospital operating procedures will be adhered to. Healthcare professional			x	Planning research to minimise risks Effective means of communication University support mechanisms Use of consent forms Staff training etc.	N/A		

No.	Hazards identified	People at risk from hazards	Existing control	Н	Risk M	L	Further action / recommendations	Action by whom	Action by when	Completed
			research is by telephone.					- ,s	5,	
3	Driving	Researcher	Researchers may drive personal vehicle to the hospital or take public transport.			x	Compliance with road traffic legislation Adequate insurance for car business use – to be checked by PI	N/A		
	Lone Working- Miscellaneous Hazards Difficulties in summoning help when required; risk of abuse/attack	Researcher	Patient research will take place in hospital environment so existing hospital operating procedures will be adhered to. Healthcare professional research is by telephone.			x	 Where possible carry a mobile phone. Leave details of the field site and a work plan (include contact name and address) with colleagues in the department or at home prior to any trip. Specify dates and times of departure and return. If your plans change, inform someone as soon as possible. Do not carry valuables or large sums of money unless you need to. Carry a personal alarm (This advice is directed to males as well as females - all are equally vulnerable when alone!) Instigate a "check-in" system with a colleague or supervisor - Phone in at regular intervals. If you do not phone or return at a certain time arrange for suitable action to be taken. 	N/A		

No.	Hazards identified	People at risk from hazards	Existing control	Н	Risk M	L	Further action / recommendations	Action by whom	Action by when	Completed
							Trust your intuition - If you feel scared or uneasy, do not ignore it.			
	Lone Working-Travelling alone On foot - risks of personal attack/abuse	Researcher	Researcher may travel alone by public transport and may walk between public transport stop and hospital			x	 Whenever possible avoid walking alone at night. Keep to busy, well lit roads. Avoid poorly lit or rarely used underpasses. Walk facing on-coming traffic to avoid kerb-crawlers. Do not use a personal stereo - you will be unable to hear anyone approaching from behind. Plan your journey in advance - tell someone which route you mean to take and estimated time of arrival at your destination. Walk with confidence and purpose - try not to look as if you are not sure of where you are going. Make sure wallets, cameras, jewellery and expensive watches and other valuables are not on display. Dress appropriately - try to fit in without attracting attention. 	N/A		
	Lone Working-Travelling alone By Car		Researchers may drive personal vehicle to the hospital or take public transport.			x	 Make sure the vehicle is in good working order before setting off. Make sure you have change for a telephone in an emergency. Plan your journey in advance - tell someone which route you 	N/A		

No.	Hazards identified	People at risk from hazards	Existing control	Н	Risk M		Further action / recommendations	Action by whom	Action by when	Completed
							 mean to take and estimated time of arrival at your destination. Do not leave valuables visible in the car - even when you are in it. Keep bags etc. out of reach of open windows. When parking in daylight, consider what the area will be like after dark. When returning to the vehicle, quickly look around it to make sure there is no one waiting for you. If you are forced to stop by another car, stay in the car, lock the doors and speak through a slightly open window. Make sure you know what to do if the car breaks down. (i.e. who to phone; where to phone from etc.) 			
	Lone Working- Staying in Hotels		There is no overnight stays involved in this study			x		N/A		
	Other people's homes Risk of personal attack/abuse	•	No homes will be visited during this study			x		N/A		
	Aggressive Behaviour	•	Patient research will take place in hospital environment so existing hospital operating			x	 Do not underestimate the importance of body language. Talk yourself out of problems; placate rather than provoke. 	N/A		

No.	Hazards identified	People at risk from	Existing control		Risk		Further action / recommendations Action Action Completed
		hazards	procedures will be adhered to. Healthcare professional research is by telephone.	Н	М	L	 Do not turn your back on someone who is behaving aggressively. Stay Calm, speak gently and slowly. Do not be enticed into an argument. Avoid an aggressive stance. Crossed arms, hands on hips or raised hands will challenge and confront. Keep your distance. Never try to touch someone who is angry -this will not calm the situation. Keep your eye on potential escape routes
	Physical attack		Patient research will take place in hospital environment so existing hospital operating procedures will be adhered to. Healthcare professional research is by telephone.			x	 Try to get away as quickly as possible. Move towards a place where you know there will be other people. Carry a personal alarm - set it off as close to the aggressor's ear as possible and then throw it out of reach. Shout and scream - shout something practical like "call the police!" or "Fire!" - people rarely react to cries of "help!" or "rape!" If grabbed and unable to break free - pretend to vomit. This will often have the desired effect!

No.	Hazards identified	People at risk from	Existing control		Risk		Further action / recommendations	Action	Action	Completed
	Dealing with people	hazards	Patient research will take place in hospital environment so existing hospital operating procedures will be adhered to. Healthcare professional research is by telephone.	Н	M	x	 Seek training in good interview techniques. Where possible "vet" interviewees first over the phone. Conduct interviews at neutral locations or public spaces or where neither party could be at risk. Where possible conduct any interviews with an observer. Seek advice and support from local groups. Do not wear clothes that might cause offence. Always carry your ID card and be prepared to identify yourself. Consider your dress carefully - is it suitable for the location. 	N/A	by when	

Review Date:	22/12/2021	Signature:	[name]	Job Title:	Research Fellow
--------------	------------	------------	--------------	------------	-----------------

12.15 Appendix 15: Data management plan (Version 2: 05/07/22)

0. Proposal name

DEnTal Examination deteCTion of Atrial Fibrillation (DETECT-AF)

1. Description of the data

1.1 Type of study

- 1. Phase 1 includes a cross-sectional study of screening in dental clinics to identify undiagnosed AF in adults aged 65 years and over.
- 2. Phase 2 includes a qualitative study of healthcare professionals involved in the care of phase 1 study participants to explore factors that might influence sustainability of screening processes beyond the study setting.

1.2 Types of data

The study involves two phases.

Phase one will include primary quantitative data collected verbally from the subject comprised of medical history including pharmacotherapy and AF symptoms, date of birth, sex, ethnicity, address, postcode, telephone number and registered GP/GP surgery address and ECG cardiac rhythm using KardiaMobile ECG device. Additionally, a basic periodontal examination result will be collected from the patients NHS dental records via agreed NHS gatekeepers.

Phase two will include primary qualitative data collected via audio-recorded telephone semi-structured interviews of healthcare professionals involved in the care of study participants recruited in phase one. Topics will include experiences of the study, barriers and facilitators to AF screening in dental hospitals and views about follow up pathways.

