Periodontal disease (PD) is strongly associated with cardiovascular disease. A recent study highlighted the high prevalence of AF in a population who have PD.⁶ In the dental Atherosclerosis Risk in Communities Study (ARIC) cohort, 5,958 were assessed without prior AF, 754 (13%) were found to have AF.⁶ Severe PD was associated with AF on both univariable (crude HR, 1.54; 95% CI, 1.26-1.87) and multivariable (adjusted HR, 1.31, 95% CI, 1.06-1.62) analyses. Mediation analysis suggested AF mediates the association between PD and stroke. In the main ARIC cohort, 9,666 participants without prior AF were assessed for dental care use, 1558 were found to have AF (16%).⁶

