1.3 RATIONALE FOR STUDY

Date: 30/5/2022 Version: 6

AF is prevalent, affecting approximately 5% of those aged 65 years and older. Unrecognised AF is generally not associated with symptoms and raised resting heart rate. Those with unrecognised AF usually have stroke risk scores (i.e., CHA2DS2 VASc scores) high enough to warrant anticoagulation. Furthermore, registry data suggests that incidence of AF may be much higher in a population who have periodontal disease, which generates the hypothesis that there are appreciable numbers who would benefit from early recognition of AF through simple detection programmes, followed by thromboprophylaxis to prevent future stroke.

This study aims to determine the appropriateness and impact of dentistry-based screening, using innovative technology (a single/six lead ECG device, KardiaMobile) that has been used in numerous AF screening studies, focused on identifying people with undiagnosed AF, with onward referral to their GP for appropriate medical management of AF. The study also aims to explore the role of dentists in ongoing management of AF, as well their role in raising AF awareness in the public.

The findings of this study will have broad implications for the general population aged 65 years and older with undiagnosed AF. We anticipate that the study will demonstrate that it is possible to identify and treat people in the community, not identified due to COVID-19 restrictions, who were not previously known to have AF, thus greatly reducing the risk of stroke. Findings from this study will inform the design and refinement of a future intervention for large-scale research and implementation.

2 STUDY AIM and OBJECTIVES

2.1 **Aim**

The study aims to test if dental clinics are a suitable place to identify previously undetected AF during and beyond the COVID-19 pandemic. It will determine if there is any correlation between severity of dental disease and AF incidence; test a pathway to ensure that patients are appropriately managed following detection of AF; and determine cost-effectiveness of identification of AF in dental settings.

Primary Objective:

Edinburgh Napier

• To identify the proportion of screened participants with newly identified AF in attending a dental clinic aged 65 years and older.

Secondary Objectives:

- To examine the correlation between periodontal health/disease status; age, sex; ethnicity; Index of Multiple Deprivation; and incidence of AF.

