4 STUDY PROCEDURE

4.1 STUDY ASSESSMENTS

Phase 1: patient screening:

The study nurse will complete the following screening protocol:

- The screening will be approximately 5min duration.
- Screening will consist of an initial brief medical history, including pharmacotherapy and screen of AF symptoms. We will also ask for date of birth, sex, ethnicity, postcode so that we can link Basic Periodontal Examination to participants. We will also ask for telephone number and registered GP/GP surgery address only in the case of abnormal rhythm or inconclusive rhythm so that we are able to inform the GP of results and follow up participants [Appendix 11].
- The study team will assess cardiac rhythm using the single-lead recording function on the handheld KardiaMobilie ECG device for 30s. The KardiaMobile ECG device will be the property of ENU and will be in the possession of the study nurse during assessments. The device will not be on participants personal mobile telephones.
- The ECG record with a unique identification number will be transmitted by wireless connection on a secure server to an iCloud by the KardiaMobile software. The ECG record is only accessible by the study team.
- The study team will advise the participant of the suspected diagnosis and ensure they understand the next steps in the pathway
- For every person with an abnormal ECG (not AF), the study team will offer a 6-lead ECG using the KardiaMobile 6-lead functionality. KardiaMobile

Date: 30/5/2022 Version: 6

records Leads I,II,II, AVL, AVR, and AVF by additional electrode placement on left knee or ankle.

At the end of the screening, participants will be given a participant debrief sheet [Appendix 10] and those with a normal rhythm will be given a letter stating that no further action is required [Appendix 16].

Protocol if AF is not suspected from the screening

GP will not be informed of the participant screening.

Protocol if a diagnosis of AF is suspected from the screening

• The study nurse will counsel the participant and advise that their GP will be contacted to arrange follow up.

- Edinburgh Napier University researchers will send a typed letter to the GP explaining the potential diagnosis, which will include a copy of the ECG recording. If required, the letter will include an invitation to refer their patient for a full assessment at any cardiology service of their choosing. A copy will be inserted in the patient notes at Newcastle Dental Hospital.

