5.1.2 Data analysis

Phase 1: patient screening:

Primary analyses will be conducted using SPSS (V26). New episodes of AF will be expressed as true positives divided by total number screened with accompanying 95% CIs. A sample size of 1000 will provide a CI of 60.8% assuming an incidence of 1.6%. χ^2 tests will be used to compare new cases by sex and to identify associations between AF incidence and age group or AF risk factors. A Pearson's or Spearman's correlation test, depending on normality of data, will be used to assess the strength and the direction of relationships between parameters. A two-sided p value of < 0.05 will be considered significant.

Cost-effectiveness

A previously tested decision-analytic Markov model⁸ will be used to simulate the risk of stroke and bleeding events with standard case finding of newly identified AF (i.e. no screening/usual care) and to then assess the impact that screening with single lead ECG would have on the downstream costs and health outcomes over a 30 year time

Edinburgh Napier

horizon. Costs incorporated in the model will include those associated with screening, drugs to offset the risk of stroke (i.e., warfarin or NOACs), adverse events (e.g., systemic embolism, stroke) and the potential complications of warfarin and NOAC treatment (e.g., intracranial haemorrhage, clinically relevant bleed). Health-state utilities associated with pre and post treatment will be incorporated in the model to calculate QALYs. A ceiling ratio of £30,000 per QALY to delineate the cost-effectiveness of opportunistic screening will be applied. Costs and benefits (QALYs) will be discounted at the NICE recommended rate of 3.5% per annum in line with the NICE reference case. Model inputs will be based on several available evidence sources including previous work in AF screening in Scotland. Extensive deterministic sensitivity analysis along with probabilistic sensitivity analysis will be undertaken to investigate model assumption and parameter uncertainty on robustness of the results.

Phase 2: healthcare professionals' interview:

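### Smoking is not recorded on any data-collection list, so the planned dataset cannot show whether a periodontal-AF association is independent of smoking

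*Combined protocol and SAP*

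**What the plan says.** The aim (section 2.1) includes the periodontal question: "It will determine if there is any correlation between severity of dental disease and AF incidence". The first secondary objective repeats it and adds age, sex, ethnicity and deprivation.

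Data capture is described in four places:

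- Section 4.1: "Screening will consist of an initial brief medical history, including pharmacotherapy and screen of AF symptoms", plus date of birth, sex, ethnicity and postcode.
- Section 5.1.1: essentially the same list, with postcode converted to a deprivation quintile.
- Appendix 15, section 1.2: "medical history including pharmacotherapy and AF symptoms, date of birth, sex, ethnicity, address, postcode, telephone number and registered GP/GP surgery address", together with the ECG rhythm and the Basic Periodontal Examination (BPE).
- Appendix 11, the form itself: tick-boxes for heart failure, hypertension, stroke/TIA/thromboembolism, vascular disease, diabetes and AF, then named drugs, symptoms, rhythm result and BPE.

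The only item to be supplied from the dental record is the BPE (section 4.1). The one-month call is for participants with suspected AF or another abnormal rhythm, and its form (Appendix 12) covers referral, 12-lead ECG, medication and procedures.

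Section 5.1.2 plans χ² tests and Pearson or Spearman correlations, with the rule "A two-sided p value of < 0.05 will be considered significant". It describes no adjusted model.

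The background (section 1.1) cites a cohort in which "Severe PD was associated with AF on both univariable (crude HR, 1.54; 95% CI, 1.26-1.87) and multivariable (adjusted HR, 1.31, 95% CI, 1.06-1.62) analyses".

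**The concern.** If smoking contributes to both gum disease and AF, people with severe periodontal disease will show more AF even where the gum disease itself adds nothing. Regression, stratification and matching can deal with this only if smoking was recorded.

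The protocol does not treat the association as purely descriptive. Section 1.2 attributes raised cardiovascular risk to periodontal disease, section 1.3 builds the study hypothesis on higher AF incidence in that group, and section 1.1 relies on adjusted and mediation results. A positive finding here would invite the same reading, and the dataset could not answer the reply that it reflects smoking. Appendix 15 (sections 5.1 and 5.2) plans to make the data open, so the gap would pass to later users.

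**Working it through.** **1. Is smoking really absent?** None of the lists in sections 4.1 and 5.1.1, Appendix 11, Appendix 12 or Appendix 15 section 1.2 contains a smoking or tobacco item. The wording in the protocol body and in Appendix 15 is general (medical history) and would not settle the matter alone. Appendix 11 does: its history block is a closed tick-list with no free-text field.

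**2. Could the plan supply it later?** Not as written. The follow-up call excludes participants with a normal trace, who will be the large majority, and its form has no smoking item. The dental hospital returns only the BPE.

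**3. The plan's own precision figure and the number of cases.** Section 5.1.2 takes n = 1000, "assuming an incidence of 1.6"%, and 95% confidence intervals. The stated precision appears as 60.8% in the extracted text and is most plausibly ±0.8%.

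- Wald half-width = 1.96 × √(0.016 × 0.984 / 1000) = 0.0078, or 0.8 percentage points. The figure reproduces on that reading.
- Expected new cases = 1000 × 0.016 = 16.

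**4. How much does adjustment matter in the cited cohort?**

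- ln(1.54) = 0.432 and ln(1.31) = 0.270.
- Fall on the log scale = 1 − 0.270/0.432 = 37%.

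This is the total change from all covariates, which the protocol does not list.

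**5. How much could smoking alone do?** The documents give no smoking figures, so these inputs are assumptions: smoking prevalence p1 = 20-30% with severe disease and p0 = 10% without, and AF risk ratio for smoking RR = 1.3-2.0. If the true association is null, the apparent one is

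(1 + p1(RR − 1)) / (1 + p0(RR − 1))

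| p1 | RR | Apparent ratio |
|---|---|---|
| 20% | 1.3 | 1.06/1.03 = 1.03 |
| 30% | 1.3 | 1.09/1.03 = 1.06 |
| 20% | 2.0 | 1.20/1.10 = 1.09 |
| 30% | 2.0 | 1.30/1.10 = 1.18 |

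Against the cited adjusted effect, ln(1.03)/ln(1.31) = 11% (using the unrounded 1.029) and ln(1.18)/ln(1.31) = 62% (using 1.182). A wider assumed range, from 15% against 8% with RR 1.2 up to 60% against 30% with RR 2.0, gives 1.01 to 1.23.

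**6. How precise would any estimate be?** Assume half of participants have severe disease, and no association.

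- SE of the log odds ratio = √(1/8 + 1/8 + 1/492 + 1/492) = 0.504.
- The 95% CI is the estimate multiplied and divided by exp(1.96 × 0.504) = 2.7.

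With a 30:70 split either way the SE is 0.550 and the factor 2.9. Two-sided power at 0.05 for a crude risk ratio of 1.31 to 1.54 is about 6% to 16% when 30-70% have severe disease.

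**The case against.** The strongest reply is that the protocol asks only for a correlation. For deciding where to screen, the crude association is what counts: a clinic whose patients have more AF is a better place to look, whatever the reason. That stands. A reader might infer that the secondary objective cannot be met at all, but the documents do not support this, because the correlation as worded can be estimated and reported.

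Second, precision is the larger limit. A bias factor of 1.03-1.18 is small beside an interval spanning a factor of 2.7-2.9 each way. That also stands, and it restricts what adjustment can deliver. It does not justify leaving the item out: imprecision is visible in the interval and can be reduced by pooling with the larger research that section 1.3 anticipates, whereas more participants without smoking data leave the bias in place.

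Two other tempting readings go too far:

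- That 37% of the cited association was confounding. The covariates are not listed. Smoking may or may not be among them, and some may lie on the causal pathway. The figure shows that adjustment in general matters; it is not smoking's share.
- That the information is lost for good. Participants are identifiable and linked to dental records under consent, so retrieval under an amendment is conceivable, although the documents do not say whether those records hold smoking status. A sensitivity analysis like step 5 could bound the bias. Deprivation, hypertension and vascular disease are partial proxies.

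**Conclusion.** The omission is confirmed, and it limits interpretation of a secondary objective. On the data the plan collects, the periodontal-AF association cannot be adjusted for smoking, so it could not be presented as independent of it. The primary proportion is untouched.

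The size is uncertain. Under the assumed inputs, smoking alone could move a null association to about 1.03-1.18, from negligible up to roughly three-fifths of the log of the cited adjusted effect. This rests on smoking being a shared cause, which is general subject knowledge, and on prevalences and a risk ratio that the documents do not give.

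The change is worth making because the interview already takes place and the item is nearly free. It will not by itself give a firm answer: about 16 new cases are expected, and section 5.1.2 has no adjusted analysis in which to use it.

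**What to change.** - **Form and data lists.** Add one item (current, former or never smoker) to Appendix 11, and name it in sections 4.1 and 5.1.1 and in Appendix 15 section 1.2.
- **Analysis (section 5.1.2).** Report the periodontal-AF odds ratio with its 95% CI, unadjusted and, labelled exploratory, adjusted for a small set fixed in advance: for example age and ever/never smoking, by penalised logistic regression. With periodontal status as one term this is three parameters on about 16 events, or 5.3 events each. Three-level smoking plus age, sex and periodontal status would be five parameters, or 3.2 events each, which is too many.
- **Interpretation.** State beforehand that the expected case count makes both estimates imprecise, and that the unadjusted figure describes co-occurrence only.

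The cost is a few seconds in a screen of about 5 minutes, a minor amendment by the route in section 9.1, and a somewhat wider interval for the adjusted estimate. Collapsing smoking to ever/never leaves some residual confounding, which should be acknowledged. If recruitment has started, report how many participants lack the item.
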